7.1.2. Part B

Statistical Analysis Plan, Version 2.0

Date Issued: 03APR2024

Visit Number		1	2	3	4	5
Type of Visit	С	С	SC	С	SC	SC/C
Month Timepoint				M1	M3	M6
Visit Day	Screening ^a	D1 (Baseline)	D8	D29	D91	D181/ EoS
Window Allowance (Days)	-28	N/A	+3	-7 to +3	±5	±14
Informed consent form, demographics, concomitant medications, medical history ^b	Х					
Inclusion/exclusion criteria	Х	Х				
Physical examination ^b	Х					
Vital signs measurements	Х	Х				
Pregnancy testing	Х	Х				
Randomization		Х				
Blood collection for humoral immunogenicity		Х		Х		Xi
Study intervention dosing (including 30-minute, post-dose observation period)		Х				
eDiary activation for recording solicited ARs/medication recording (7 days) ^d		X				
Follow up safety call ^e			Х		X	Xi
Review of solicited ARs and medication eDiary		X	Х			
Recording of unsolicited AEs		X	Х	X		

Statistical Analysis Plan, Version 2.0

mRNA-1010-P303

Date Issued: 03APR2024

Visit Number		1	2	3	4	5
Type of Visit	С	С	SC	С	SC	SC/C
Month Timepoint				M1	M3	M6
Visit Day	Screening ^a	D1 (Baseline)	D8	D29	D91	D181/ EoS
Window Allowance (Days)	-28	N/A	+3	-7 to +3	±5	±14
Recording of SAEs, AESIs, MAAEs, AEs leading to discontinuation from study participation, and concomitant medications/procedures relevant to or for their treatment ^f		X	Х	Х	Х	X
Recording of concomitant medications ^g		Х	Х	Х		
Recording of non-study vaccinations ^h		Х	Х	Х	Х	Х
Recording of concomitant procedures/surgeries		Х	Х	Х	Х	Х
Study completion						Х

Abbreviations: AE = adverse event; AESI = adverse event of special interest; AR = adverse reaction; C = clinic/in-person visit; D = day; eDiary = electronic diary; EoS = end of study; IM = intramuscular(ly); M = month; MAAE = medically attended adverse event; SAE = serious adverse event; SC = safety call (or contact by electronic means).

^a. The Screening Visit and Day 1 may be performed on the same day or a different day. Additionally, the Screening Visit may be performed over multiple visits if within the 28-day screening window.

^b. Verbal medical history is acceptable. Clinically significant findings during the Screening Visit physical examination should also be recorded in the participant's medical history.

^c. See Section 3.3.1, Table 7 for dose levels and treatment groups.

^d. The eDiary entries will be recorded at approximately 30 minutes after study intervention dosing while at the clinic with instruction provided by the clinic staff. Study participants will continue to record in the eDiary for solicited ARs each day after they leave the clinic, on the day of study intervention dosing and the subsequent 6 days following study intervention dosing.

^e. An unscheduled follow-up safety call may be triggered by the identification of a relevant safety event from an eDiary record, or other participant contact. A safety phone call may trigger an unscheduled visit.

^f. Trained clinic staff will call (or contact by electronic means) all participants to collect information relating to any MAAEs, AEs leading to discontinuation from study participation, SAEs, AESIs, information on concomitant medications associated with those events, and any nonstudy vaccinations.

mRNA-1010-P303

Statistical Analysis Plan, Version 2.0

Date Issued: 03APR2024

^g. All concomitant medications will be recorded from Day 1 through Day 29; thereafter, only concomitant medications relevant to or for the treatment of an SAE, AESI, or MAAE will be recorded through Day 181 (Month 6)/EoS.

^h. All non-study vaccinations will be recorded through 181 days after the dose of study intervention.

ⁱ. Samples for humoral immunogenicity on Day 181 (Month 6)/EoS will be collected for first 1000 participants and analyzed in a subset. Participants in the subset require a clinic visit on Day 181 (Month 6)/EoS for sample collection. All other participants will require a safety call.

mRNA-1010-P303

7.1.3. Part C

Statistical Analysis Plan, Version 2.0

Date Issued: 03APR2024

Visit Number		1	2	3	4	5
Type of Visit	С	С	SC	С	SC	SC/C
Month Timepoint				M1	М3	M6
Visit Day	Screening ^a	D1 (Baseline)	D8	D29	D91	D181/ EoS
Window Allowance (Days)	-28	N/A	+3	-7 to +3	±5	±14
Informed consent form, demographics, concomitant medications, medical history ^b	Х					
Inclusion/exclusion criteria	Х	Х				
Physical examination ^b	Х					
Vital signs measurements	Х	Х				
Randomization		Х				
Blood collection for humoral immunogenicity		Х		Х		Xi
Study intervention dosing (including 30-minute, post-dose observation period)		Х				
eDiary activation for recording solicited ARs/medication recording (7 days) ^d		Х				
Follow up safety call ^e			X		X	Xi
Review of solicited ARs and medication eDiary		Х	Х			
Recording of unsolicited AEs		Х	Х	Х		

Statistical Analysis Plan, Version 2.0

mRNA-1010-P30)3
---------------	----

Date Issued: 03APR2024

Visit Number		1	2	3	4	5
Type of Visit	С	С	SC	С	SC	SC/C
Month Timepoint				M1	M3	M6
Visit Day	Screening ^a	D1 (Baseline)	D8	D29	D91	D181/ EoS
Window Allowance (Days)	-28	N/A	+3	-7 to +3	±5	±14
Recording of SAEs, AESIs, MAAEs, AEs leading to discontinuation from study participation, and concomitant medications/procedures relevant to or for their treatment ^f		x	Х	X	X	X
Recording of concomitant medications ^g		Х	Х	Х		
Recording of non-study vaccinations ^h		Х	Х	Х	Х	Х
Recording of concomitant procedures/surgeries		Х	Х	Х	X	X
Study completion						X

Abbreviations: AE = adverse event; AESI = adverse event of special interest; AR = adverse reaction; C = clinic/in-person visit; D = day; eDiary = electronic diary; EoS = end of study; IM = intramuscular(ly); M = month; MAAE = medically attended adverse event; SAE = serious adverse event; SC = safety call (or contact by electronic means).

^a. The Screening Visit and Day 1 may be performed on the same day or a different day. Additionally, the Screening Visit may be performed over multiple visits if within the 28-day screening window.

^b. Verbal medical history is acceptable. Clinically significant findings during the Screening Visit physical examination should also be recorded in the participant's medical history.

^c. See Section 4.3.1, Table 9 for dose levels and treatment groups.

^d. The eDiary entries will be recorded at approximately 30 minutes after study intervention dosing while at the clinic with instruction provided by the clinic staff. Study participants will continue to record in the eDiary for solicited ARs each day after they leave the clinic, on the day of study intervention dosing and the subsequent 6 days following study intervention dosing.

^e. An unscheduled follow-up safety call may be triggered by the identification of a relevant safety event from an eDiary record, or other participant contact. A safety phone call may trigger an unscheduled visit.

^f. Trained clinic staff will call (or contact by electronic means) all participants to collect information relating to any MAAEs, AEs leading to discontinuation from study participation, SAEs, AESIs, information on concomitant medications associated with those events, and any nonstudy vaccinations.

mRNA-1010-P303

Statistical Analysis Plan, Version 2.0

Date Issued: 03APR2024

^g. All concomitant medications will be recorded from Day 1 through Day 29; thereafter, only concomitant medications relevant to or for the treatment of an SAE, AESI, or MAAE will be recorded through Day 181 (Month 6)/EoS.

^h. All non-study vaccinations will be recorded through 181 days after the dose of study intervention.

ⁱ. Samples for humoral immunogenicity on Day 181 (Month 6)/EoS will be collected for approximately the first 1000 participants and analyzed in a subset. Participants in the subset require a clinic visit on Day 181 (Month 6)/EoS for sample collection. All other participants will require a safety call.

7.2. Standards for Variable Display in TLFs

The following applies to Part A, Part B, and Part C:

Continuous Variables: The precision for continuous variables will be based on the precision of the data itself. The mean and median will be presented to one decimal place more than the original results; the SD will be presented to two decimal places more than the original results; the min and max will be presented to the same precision as the original results. For model-based estimates or immunogenicity analyses, the results may be presented up to three decimal points, unless otherwise specified.

Categorical Variables: Percentages will be presented to 1 decimal place. If the count is 0, the percentage will not be displayed. If the count equals the denominator, the percentage will be displayed as 100.

7.3. Analysis Visit Windows for Immunogenicity Analysis

The following applies to Part A, Part B, and Part C:

Immunogenicity Analysis will be summarized using the following analysis visit window for post-injection assessments:

Step 1: If the immunogenicity assessments are collected at a scheduled visit, the collected data will be mapped to the nominal scheduled visit, the data collected at scheduled visit will be used.

Step 2: If the immunogenicity assessments are not collected at the scheduled visits, assessments collected at an unscheduled visit will be used using the analysis visit windows described in Table 12 below.

Visit	Target Study Day	Visit Window in Study Day
Immunogenicit	У	
Day 1	1 (Date of Injection)	1, Pre-vaccination
Day 29	29	[2, 105]
Day 181	181	≥106

Table 12 Analysis Visit Window

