2.7.1.1. Participant Discontinuation/Withdrawal from the Study

A participant may withdraw from the study at any time at the participant's own request for any reason (or without providing any reason).

A participant may be withdrawn at any time at the discretion of the Investigator for safety, behavioral, or compliance reasons.

At the time of discontinuing from the study, if possible, the Investigator will request that the participant complete all study procedures pending at the time of withdrawal, as shown in the SoA (Table 1).

The participant will be permanently discontinued from the study participation at that time.

A participant who withdraws from the study will not be replaced.

If the participant withdraws consent for disclosure of future information, the Sponsor may retain and continue to use any data collected before such a withdrawal of consent.

If a participant withdraws from the study, the participant may request destruction of any samples taken and not tested, and the Investigator must document this in the site study records.

The Sponsor will continue to retain and use all research results that have already been collected for the study evaluation. All biological samples that have already been collected may be retained and analyzed at a later date (or as permitted by local regulations).

From an analysis perspective, a "withdrawal" from the study refers to a situation wherein a participant does not return for the final visit foreseen in the protocol. All data collected until the date of withdrawal or last contact of the participant will be used for the analysis. A participant is considered a "withdrawal" from the study when no study procedure has occurred, no follow up has been performed, and no further information has been collected for that participant from the date of withdrawal or last contact.

Information relative to the withdrawal will be documented in the eCRF. The Investigator will document whether the decision to withdraw a participant from the study was made by a participant, or by the Investigator, as well as which of the following possible reasons was responsible for withdrawal:

- Adverse event
- Death
- LTFU
- Noncompliance with study procedures
- Physician decision
- Pregnancy
- Protocol deviation
- Study terminated by Sponsor
- Withdrawal by participant
- Withdrawal due to solicited AR/reactogenicity
- Other

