2.4. Analysis Sets

The analysis sets are defined in Table 2.

Table 2 Populations for Analysis

The following analysis populations apply to Part A, Part B, and Part C, unless otherwise specified:

Population	Description

Randomization Set	All participants who are randomly assigned to the treatment, regardless of the participants' treatment status in the study.	
	Participants will be analyzed according to the treatment group to which they were randomized.	
Full Analysis Set	All participants in Randomization Set who received any study vaccination.	
	Participants will be analyzed according to the treatment group to which they were randomized.	
Immunogenicity Set	All participants in the FAS who have baseline and Day 29 antibody assessment via HAI assay.	
	Participants will be analyzed according to the treatment group to which they were randomized.	
PP Immunogenicity Set	The PP Immunogenicity Set includes all participants in the Immunogenicity Set who received the planned dose of study intervention, complied with the immunogenicity testing schedule for baseline and Day 29 *, and had no significant protocol deviations that impact key or critical data. Participants with RT-PCR-confirmed influenza between Days 1 to 29 will be removed from the PP Immunogenicity Set (Part A only). The PP Immunogenicity Set will be used for all analyses of	
	immunogenicity unless otherwise specified. Participants will be analyzed according to the treatment group to which they were randomized.	
Solicited Safety Set	All participants in the FAS who contributed any solicited AR data.	
	The Solicited Safety Set will be used for the analyses of solicited ARs, and participants will be included in the treatment group corresponding to the study intervention that they actually received.	
Safety Set	All participants in the FAS.	
	The Safety Set will be used for all analyses of safety except for the solicited ARs. Participants will be included in the treatment group corresponding to the study intervention that they actually received.	

Abbreviations: AR=adverse reaction; FAS=Full Analysis Set; HAI=hemagglutinin inhibition; PP=per protocol; RT-PCR=reverse transcription polymerase chain reaction.

* Complied with the immunogenicity testing schedule for baseline and Day 29 is defined as having immunogenicity samples collected before the IP administration and between Day 22 and Day 43 (i.e., -7/+14 days of Day 29).

ModernaTX, Inc. mRNA-1010-P303

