2.5.3.5. Analysis of Exploratory Endpoints

• GMT at Day 181 as measured by HAI

ModernaTX, Inc. mRNA-1010-P303

Descriptive statistics (n, median, min, max) will be provided for the GMT of HAI titers with corresponding 95% CI at Day 181. The 95% CIs will be calculated based on the t-distribution of the log-transformed values then back transformed to the original scale for presentation.

• Proportion of participants reaching seroconversion at Day 181 as measured by HAI

The number and percentage of participants with seroconversion at Day 181 will be provided with 2-sided 95% CI using the Clopper-Pearson method.

For GMT and seroconversion at Day 181, the analyses will be based on participants in PP Immunogenicity Set who also had immunogenicity sample(s) collected between Day 167 and Day 195 (i.e., between -/+ 14 days of Day 181).

- GMT and GMFR of nAbs by assays such as MN assays or alternative methods against vaccine-matched or vaccine-mismatched strains on Day 29 compared with Day 1 (Baseline)
- GMT and GMFR of anti-HA antibodies as measured by HAI against vaccine mismatched strains on Day 29 compared with Day 1 (Baseline).

Descriptive statistics (n, median, min, max) will be provided for these endpoints with corresponding 95% CI at each time point. The 95% CIs will be calculated based on the t distribution of the log-transformed values then back transformed to the original scale for presentation. In addition, the GMT and GMFR with corresponding 95% CI will be plotted at each time point respectively.

• Assessment of immune responses in participants with RT-PCR-confirmed protocoldefined ILI.

A protocol-defined ILI is determined by the occurrence of at least 1 respiratory illness symptom concurrently with at least 1 systemic symptom, or the occurrence of any 2 or more respiratory symptoms, as shown in Table 6.

An RT-PCR confirmed protocol-defined ILI is defined as a positive influenza result on a respiratory sample by RT-PCR performed at the Global Central Laboratory and/or a local

certified laboratory within 7 days of onset of protocol-defined ILI at any time during the study period.

Respiratory symptoms	Systemic symptoms
Sore throat	Body temperature ≥37.5°C [≥99.5°F]
Cough/rhinorrhea/nasal congestion (≥1 of	Chills
the 3 symptoms count as 1 respiratory	Tiredness
symptom)	Headache
Sputum production	Myalgia
Wheezing	Nausea/vomiting
Difficulty breathing	Diarrhea

Table 6 Respiratory and Systemic Symptoms for Protocol-defined ILI (Part A)

CCI	
	_

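### SAP 7.3 lets a blood taken as early as Day 2 count as the Day 29 titre in the supplementary coprimary analysis, against the SAP's own handling of discontinuation before Day 29

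*SAP*

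**What the plan says.** SAP 7.3, which applies to all three parts, has two steps. Step 1 covers samples from a scheduled visit: "the collected data will be mapped to the nominal scheduled visit". It states no study-day limit. Step 2 is a fallback for when no scheduled-visit sample was collected: "assessments collected at an unscheduled visit will be used using the analysis visit windows described in Table 12 below". There Day 29 runs from Day 2 to Day 105, and Day 181 is anything from Day 106.

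SAP 2.4 defines the Immunogenicity Set as "All participants in the FAS who have baseline and Day 29 antibody assessment via HAI assay", with no day range. The PP Immunogenicity Set adds compliance with the testing schedule, which a footnote to Table 2 defines as a pre-dose baseline and a second sample "between Day 22 and Day 43". SAP 2.5.3.2, 3.5.3.2 and 4.5.3.2 repeat the primary analyses on the Immunogenicity Set.

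For a participant who leaves the study, Protocol 2.7.1.1 says that, if possible, "the Investigator will request that the participant complete all study procedures pending at the time of withdrawal". Sections 3.7.2 and 4.7.2 carry this to Parts B and C.

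SAP 7.8 (Table 16) names discontinuation or unrelated death before Day 29 as intercurrent event IcEv1. Tables 17 to 19 handle IcEv1 by principal stratum in the supplementary Estimands 1b and 2b, as in the primary estimands.

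For the exploratory Day 181 summaries, SAP 2.5.3.5 (Part A) restricts samples to those taken "between Day 167 and Day 195". SAP 3.5.3.5 (Part B) has no such limit, and none is stated for Part C.

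**The concern.** The Immunogenicity Set repeat is the only planned rerun of the coprimary analyses on another analysis set, so a reader will use it to judge whether the PP result is robust. Under the mapping rule, a participant bled a few days after dosing can contribute that value as a Day 29 titre. Such a value is essentially the baseline: it counts as a failure to seroconvert and pulls the arm's GMT towards baseline.

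Withdrawal because of reactogenicity is a listed reason in Protocol 2.7.1.1, so the two arms need not supply such samples equally. Apart from any numerical effect, the mapping rule and the stated estimand disagree about who belongs in the analysis.

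**Working it through.** **1. The plan's own figure.** Part C overall power is stated as about 93% (SAP 4.3.3). Inputs: 1275 per group, 1-sided 0.025, GMR 0.90, SD 1.5 on the natural-log scale, margin 1.5; SCR 58% vs 60% (A) and 48% vs 50% (B), margin 10 points.
- GMT, one strain: Φ[(ln 0.90 + ln 1.5)/(1.5·√(2/1275)) − 1.96] = 0.999; four strains, 0.996.
- SCR: Φ[(pT − pC + 0.10)/√((pT(1−pT) + pC(1−pC))/1275) − 1.96]; product over four strains, 0.933.
- Overall, treating strains as independent: 0.996 × 0.933 = 0.929.

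This agrees with the plan and is not in dispute.

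**2. The windows side by side.**
- Schedule of Activities, −7 to +3 days: Day 22 to Day 32.
- PP Immunogenicity Set, −7/+14 days: 29 − 7 = 22 to 29 + 14 = 43, which is 22 study days.
- Table 12, Step 2: Day 2 to Day 105, which is 104 study days.
- Step 1: no limit.

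The upper limit of 105 is the midpoint of Days 29 and 181: (29 + 181)/2 = 105. The lower limit of 2 is not the midpoint of Days 1 and 29: (1 + 29)/2 = 15.

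**3. A Day 3 withdrawal traced through the rules.**
- Blood recorded as unscheduled: no scheduled sample exists, Step 2 applies, and Day 3 lies in Day 2 to 105, so it becomes Day 29.
- Blood recorded under the nominal Day 29 visit: Step 1 applies, and it becomes Day 29.
- PP Immunogenicity Set: Day 3 is before Day 22, so the participant is excluded.
- Immunogenicity Set: baseline and a Day 29 result both exist, so the participant is included.
- Estimands 1b and 2b: discontinuation before Day 29 is IcEv1, so the participant is outside the principal stratum.

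The last two lines cannot both hold.

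**4. Size if the early samples fall in one arm.** Assumptions, none given in the documents: k = 10 to 30 early samples, about 1400 in the arm (between 1275 in the PP set and 1500 randomized in Parts B and C), early titre equal to baseline, true 4-fold rise. The SCR of 58% is the plan's value for A strains in the mRNA-1010 arm.
- SCR change = −0.58 × k/1400: −0.41 points at k = 10, −1.24 points at k = 30.
- Crude GMT factor = 4^(−k/1400): 0.990 at k = 10, 0.971 at k = 30, a fall of 1.0% to 2.9%.

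**5. Size if both arms are affected equally.** Let f be the assumed share of early samples in each arm. SCR differences and log GMR shrink by (1 − f). At f = 2%, a true difference of −10 points becomes −10 × 0.98 = −9.8, and a true GMR of 0.667 becomes 0.672. With 1400 per arm and SCR 50% vs 60%, one-sided error at the margin in the supplementary analysis is:
- f = 1%: 0.028 (SCR), 0.030 (GMT).
- f = 2%: 0.032 (SCR), 0.035 (GMT).

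Nominal is 0.025. The range in item 4 corresponds to 10/1400 = 0.7% up to 30/1400 = 2.1% of an arm.

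**The case against.** The strongest reply is that little depends on this. Success is judged on the PP Immunogenicity Set, and the supplementary repeat has no success criterion. That stands.

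The route is also inferred. The request at withdrawal is made only if possible, and whether a draw not due for weeks is pending on Day 3 is open to interpretation. The Schedule of Activities plans no immunogenicity blood at unscheduled visits, and Protocol 2.8 allows repeat or unscheduled samples only for safety or technical reasons. So numbers are probably small. The rule still admits such a sample if one is taken.

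It can also be said that the estimand already excludes the early withdrawal through IcEv1. The target does; the set definition and mapping rule that programmers will follow do not. The target-population wording in Estimands 1b and 2b speaks of complying with blood sampling, which might be read as importing Day 22 to 43, but the footnote defines a differently worded condition belonging to the PP set alone.

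Finally, the supplementary analysis is meant to be broader, reflecting imperfect compliance, so holding it to the PP upper limit of Day 43 would remove part of that contrast. This also stands: a late sample is a mistimed response, whereas a Day 3 sample precedes any response.

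A reader might infer that every unscheduled sample between Day 2 and Day 105 is treated as Day 29. The documents do not say that, because Step 2 applies only when no scheduled-visit sample exists. For an early withdrawal, though, that is the usual situation.

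**Conclusion.** The point holds for the supplementary analysis of the eight coprimary endpoints in Parts A, B and C. As written, the mapping rule and the Immunogenicity Set definition can admit a pre-response titre as a Day 29 result, contrary to the principal-stratum handling of IcEv1. The inconsistency exists whatever the count; the numerical effect depends on it. Under the stated assumptions it is about 0.4 to 1.2 SCR points and 1% to 3% in GMT in the affected arm, small against margins of 10 points and 1.5-fold, and nil if there are no such samples.

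A reader might infer that the noninferiority conclusions are at risk. They are not, because the Day 22 to 43 rule protects the primary analysis. Nor do the documents show a bias in favour of mRNA-1010: an excess of early samples in that arm would lower its response and work against noninferiority, while balanced early samples would shrink differences slightly and make the supplementary check a little too lenient. The direction is unknown.

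**What to change.** Require a Day 29 sample to be taken no earlier than Day 22, the earliest day that both the Schedule of Activities and the PP rule accept. State this in the Immunogenicity Set definition (SAP 2.4), or apply it to both steps of SAP 7.3, with the Table 12 lower limit changed from 2 to 22. Editing Table 12 alone is not enough, because Step 1 would still pass a withdrawal blood entered under the Day 29 visit. Align the wording with IcEv1, including how to treat someone sampled from Day 22 who discontinues before Day 29. List earlier samples without analysing them as Day 29.

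For the exploratory Day 181 summaries in Parts B and C, carry over Part A's Day 167 to 195 limit. Whether to cap the supplementary Day 29 window at Day 43 is the sponsor's choice.

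The cost is a short SAP edit and a few participants leaving the supplementary set. For Part A, whose primary results are already known (Protocol 5.7.1), the change would be post hoc and should be labelled so.
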